6.0 Procedures Involved*

PROTOCOL TITLE:

Making Treatment Decisions Using Genomic Testing

6.1 This is a feasibility and efficacy study. Two participant interviews will be conducted by the study staff. Audio recordings will be collected of patient-physician encounters using the QPL over a month time span.

6.2 Eligible patients will be contacted by study staff via phone call. The study staff will describe the study, answer questions, obtain verbal consent, and complete the first, T1 interview before the patient receives *Oncotype DX* results. After obtaining a signed informed consent and HIPAA authorization by mail, the QPL will be provided to the patient. They will receive the QPL by mail or email, depending on their preference, before their Score disclosure appointment. Study staff will be available to audio record the patient-physician encounter during their appointment. The second, T2 interview will be done after patients receive their test results but prior to initiation of adjuvant chemotherapy.

6.3 The risks of participation are minimal. The survey elements have been designed to minimize emotional distress. A distress protocol has been put in place to refer subjects to psychological consult when appropriate. It is possible that participants will derive benefit from the use of the QPL in how they communicate with their physician and make decisions regarding treatment options.

6.4 Measures will include:

Sociodemographics. We will assess age, race/ethnicity, education, marital, employment, income, insurance status, comorbidity, and family cancer history.

Disease variables and treatments. We will assess diagnosis date, pathology (staging, grade, ER/PR/HER2), treatments, and dates.

Oncotype DX Recurrence Score. We will assess the Recurrence Score and the related category.

Chemotherapy Selection. In our work, 95% of women make definitive treatment decisions by T2. If not, this will be noted and the interview will continue. *Data will be confirmed in the medical record.*

Self-Reported Measures:

Table 1. Variables and Data Sources		Timepoint		
Variable	Measure/source	T1	Encounter	T2
Controlling and Clinical Variables				
Sociodemographics		X		
Disease Variables, Treatments	Self-report and chart review	X		X
Recurrence Score	Self-report and chart review			X
Outcomes and Mediators				
Chemo. Selection	Self-report and chart review			X

PROTOCOL TITLE:
Making Treatment Decisions Using Genomic Testing

Chemo. Preferences	Preferences	X		X

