Comprehension	Adjuvant treatment, Recurrence Score, treatment implications	X		X
Coding of clinical encounters	RS- and treatment related information, shared decision making, patient active participation and patient-centered communication		X	X
Decisional Satisfaction	SDS			X
Communication Quality	Makoul et al.			X

Chemotherapy Preferences. We will assess preferences for chemotherapy by assessing the perceived pros (8 items) and cons (8 items) of treatment as we do in our ongoing work. Women rate the importance of each item on a scale from 1 (*Not at all important*) to 4 (*Very important*). Ratings are averaged to create scales, with higher scores indicating greater importance of pros and cons. Internal reliability is high for pros-cons, with scores above zero indicating a preference for chemotherapy. Preference concordance will be determined through a match between post-Score preference and treatment received.

Comprehension. We will assess comprehension of adjuvant treatment, Recurrence Score and category, and treatment implications (*The Test helps women decide about chemotherapy (Y/N)*). We will apply existing comprehension items, in which patients average 70% correct.¹⁴

Satisfaction. We will assess Decisional Satisfaction with the valid and reliable 6-item Satisfaction with Decision Scale, rated on a 5-point Likert scale (*Strongly agree/ disagree*), with a higher score indicating greater satisfaction. The measure has been used to assess satisfaction with breast cancer adjuvant treatment decisions.¹⁹

Perceived communication quality. We will assess patients' perceptions of quality of patient-physician communication using a 7-item scale from 1 (*Very strongly disagree*) to 6 (*Very strongly agree*). This scale has good reliability and validity and we have used this measure in our current observational study. Items are relevant to chemotherapy decisions (*The doctor fully explained the risks of treatment recommended*). Patients will respond to these regarding their primary Medical Oncologist.²⁰

Oncologist variables. We will record race, ethnicity, and gender of the patient's primary medical oncologist for our measurement of concordance.

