11.0 Vulnerable Populations*

- 11.1 Pregnant women, students, those economically disadvantaged and employees will not be excluded from this study if they are otherwise eligible to participate. We will ensure that all informed consent such

PROTOCOL TITLE:
Making Treatment Decisions Using Genomic Testing

that they will be asked to repeat back the purpose of the study after a member of the study team has gone over written informed consent. In addition, although we will be providing incentives for participation in the form of a gift card the incentives are not so large as to be coercive.

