17.0 Data Management* and Confidentiality

17.1 We will calculate descriptive and frequency distributions for all variables. We will assess the quality of the data and evaluate the extent and impact of missing data. For categorical variables, we will use Chi-Square tests or Fisher's exact tests if needed. We will test continuous variables with Student t-tests or Mann-Whitney U tests for non-normal data. Any variable that exhibits a $p < .10$ association with the key predictors or outcomes will be controlled in multivariable analyses. Potential covariates include sociodemographic and clinical variables as well as differenced.

Our primary endpoint is the percentage of patients activated via a question prompt list intervention. Women will demonstrate significant increase in comprehension from pre- to post-QPL.

Using a 2-tailed $\alpha = 0.05$ and assumed a minimum of 75 participants at T2 and accounting for clustering by oncologist, we calculated effective sample sizes assuming an average cluster size of 10 patients per oncologist and an ICC of 0.02. This reduces the sample size by a factor of 1.18, leaving an effective $N = 64$ at T2. We will have 80% power to detect changes in mean comprehension of 0.4 SD assuming a correlation of 0.5 between pre- and post- scores. We will use multilevel models to address the clustering of observations within patients and of patients within oncologists. These mixed effects regression models will include random effects for patient and oncologist and fixed effects for time, the main predictor, and covariates. The multilevel model for 2a will be a linear model and we will estimate the adjusted mean change in comprehension and the corresponding 95% confidence interval. We will estimate an adjusted odds ratio with the corresponding 95% confidence interval.

17.2 Data collected in this study will be used exclusively for research purposes; it will be managed and stored according to our sites' security standards for data that require the highest possible security to ensure there will be no inadvertent disclosure. Any computers storing or accessing data collected for the study will be required to comply with these standards.

During the trial, all study data downloaded from REDCap or gathered from other sources will reside in a HIPAA-compliant study folder. Access to the study folder is provided based

PROTOCOL TITLE:

Making Treatment Decisions Using Genomic Testing

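### The comprehension change score may include items about the woman's own Recurrence Score that she cannot know at T1, so part of any rise could come from disclosure alone

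*Combined protocol and SAP*

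**What the plan says.** Section 6.4 sets the content of the measure: "We will assess comprehension of adjuvant treatment, Recurrence Score and category, and treatment implications". One item is shown, "The Test helps women decide about chemotherapy (Y/N", and the rest are described only as existing items on which patients average 70% correct. The plan does not say when, relative to disclosure, that average was observed. Table 1 marks the comprehension row, with the Recurrence Score among its contents, at both T1 and T2.

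On timing, section 6.2 has staff "complete the first, T1 interview before the patient receives *Oncotype DX* results". T2 follows disclosure and precedes any adjuvant chemotherapy.

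Table 1 also has a separate row for the Recurrence Score itself, taken from self-report and chart review, at T2 only. The text in 6.4 describes that variable as the Score and its related category, which is close to the wording used for the comprehension content.

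The Aim 2 hypothesis in section 2.2 is a significant rise in comprehension from before to after the question prompt list (QPL). Section 17.1 estimates an adjusted mean change with a linear mixed model and gives 80% power for a change of 0.4 SD. The design is single-arm. No section lists the items, says how an answer is scored when the woman has no Score yet, or defines a subset of items comparable at both interviews.

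**The concern.** A pre-post change measures learning only if the items can be answered at both times. A question such as which category her Score fell in has no knowable answer at T1. At T2 she has been told. Such an item moves from guessing to mostly correct simply because the result was disclosed, even if her grasp of adjuvant treatment or of what the test means has not changed.

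There is no control arm to absorb that rise, so it would enter the mean change in full. The Aim 2 comprehension hypothesis could then be met, in part or wholly, by women being able to repeat their result. The plan leaves open whether this happens, because it does not say whether the Score and category items concern the woman's own result or the test in general.

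**Working it through.** **Step 1: the plan's own figures.** Inputs from section 17.1: "assumed a minimum of 75 participants at T2 and accounting for clustering by oncologist"; "assuming an average cluster size of 10 patients per oncologist and an ICC of 0.02".

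- Design effect = 1 + (10 − 1) × 0.02 = 1.18.
- Effective N = 75 / 1.18 = 63.6. The plan says "This reduces the sample size by a factor of 1.18, leaving an effective $N = 64$ at T2", so this reproduces.
- With a pre-post correlation of 0.5, SD of the change = SD × √(2 × (1 − 0.5)) = 1.0 SD.
- At N = 64 and two-sided 5%, power for 0.4 SD is 89% (normal approximation) or 88% (t). The change detectable with 80% power is 0.35 to 0.36 SD. The stated 0.4 SD agrees to one decimal place, rounded in the cautious direction. It is the benchmark below.

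**Step 2: the built-in change.** Let q be the share of items that need the woman's own Score or category, p1 and p2 the proportions correct on them at T1 and T2, and SD the standard deviation of percent correct. If nothing else changes:

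Built-in change in SD units = q × (p2 − p1) / SD.

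Assumptions, none of them given by the plan for these items: p2 = 70%; SD of 15 to 25 points, the same at both interviews; p1 = 0 (no credit before disclosure), one-third (guessing among three categories) or one-half (guessing a yes/no item).

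| p1 | q | Points added | SD 25 | SD 20 | SD 15 |
|---|---|---|---|---|---|
| 0 | 10% | 7.0 | 0.28 | 0.35 | 0.47 |
| 0 | 20% | 14.0 | 0.56 | 0.70 | 0.93 |
| 1/3 | 10% | 3.7 | 0.15 | 0.18 | 0.24 |
| 1/3 | 20% | 7.3 | 0.29 | 0.37 | 0.49 |
| 1/2 | 20% | 4.0 | 0.16 | 0.20 | 0.27 |
| any | 0 | 0 | 0 | 0 | 0 |

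Example: 0.20 × (0.70 − 0.333) = 0.073; 0.073 / 0.15 = 0.49.

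**Step 3: share of items that would reach 0.4 SD.** q = 0.4 × SD / (p2 − p1), for SD of 15 to 25 points:

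- p1 = 0: 9% to 14% of items.
- p1 = 1/3: 16% to 27%.
- p1 = 1/2: 30% to 50%.

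**Step 4: effect on the test.** With built-in change d, effective N = 64 and SD of change 1.0 SD, the two-sided 5% test rejects with probability Φ(8d − 1.96) + Φ(−8d − 1.96). If nothing but the own-result items moves:

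- q = 10%, p1 = 0: 61% to 96%.
- q = 20%, p1 = 1/3: 65% to 97%.
- q = 20%, p1 = 1/2: 25% to 57%.
- q = 0: the nominal 5%.

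**The case against.** The strongest answer is that the plan never says these items ask for the woman's own result. They may ask what the Score measures or what its categories mean, which can be answered at T1. The one item shown is general knowledge of that kind. The woman's own Score is already a separate T2-only row in Table 1, which suggests the authors knew where own-result questions belong. If so, the built-in change is zero. This stands as a limit on the point: the rise is conditional. It does not remove the point, because 6.4 uses nearly the same words for the own result and for the comprehension content, and the items are not listed.

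The 70% figure is a whole-scale average with no stated timing. Its use for own-result items at T2 is this review's assumption, not the plan's.

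A reader might infer more than the documents support:

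- **That T1 and T2 use different tests, or that Score items are at zero at T1.** Table 1 lists the same content at both times, and guessing could lift T1 above zero.
- **That the example item starts at ceiling because the study title and consent talk give its answer.** The title does not name chemotherapy. Section 11.1 says participants "they will be asked to repeat back the purpose of the study", but ties this to review of the written consent, which 6.2 places after T1; sections 22.1 and 23.1 do not settle the order. A ceiling would in any case shrink the change. This gives no reason to replace the item.
- **That Aim 2 cannot be answered.** Aim 2 also covers treatment preferences, which are not affected here. The Study Summary lists these effects as secondary, and the Background calls the impact assessment preliminary.

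**Conclusion.** The point holds conditionally. The plan scores comprehension of the Score and category before and after disclosure and tests the mean change in one arm, without saying whether any item needs the woman's own result. If one or two items in ten do, the built-in rise can reach or exceed the planned 0.4 SD when T1 is at zero, and two in ten give 0.29 to 0.49 SD at one-third correct. If T1 guessing is at one-half, two in ten add 0.16 to 0.27 SD, which is below the target but not negligible. If none do, there is no built-in rise. These ranges rest on the assumed 70% at T2 and an SD of 15 to 25 points. The item list would settle which case applies.

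**What to change.** In sections 6.4 and 17.1:

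- List the comprehension items and mark which of them need the woman's own Score or category.
- Define the T1-T2 change score using only items that can be answered correctly at both interviews: adjuvant treatment, the general meaning of the test and its categories, and treatment implications.
- Score own-Score and own-category items at T2 only, check them against the chart-review Score already collected, and report them separately as percent correct.

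The cost is a few lines of scoring text, with no added visits, patients or data. If no own-result items exist, one sentence saying so closes the matter. The downside is that the expected change may be smaller than an all-item score would show, so the 0.4 SD target should be read against the restricted score. The fix does not separate the effect of the QPL from that of disclosure or the consultation; in a single arm those remain mixed.

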7.0 Data and Specimen Banking*

[figure not shown]
7.1 N/A

8.0 Sharing of Results with Subjects*

8.1 Study results will be shared with participants at the end of the study.

9.0 Study Timelines*

9.1 The participants will be enrolled for about a month. They will complete the first interview after consenting and will also complete a follow up interview right after receiving Oncotype DX results. All study activities should be completed within 2 months. Recruitment and retention are described in Figure 1.

10.0 Inclusion and Exclusion Criteria*

- 10.1 Study staff at each site will monitor electronic patient records systems that track test orders, attend weekly Breast Cancer Meetings, and coordinate with clinic staff to recruit patients they determine to be eligible.
- 10.2 Participants will be females aged 40-75 who will receive Oncotype DX testing prior to initiation of systemic treatment.
- 10.3 We will not include patients with cognitive impairment that precludes informed consent as determined by self-report, our trained study personnel, or patient records. We will also exclude those who are unable to provide consent in English.

11.0 Vulnerable Populations*

- 11.1 Pregnant women, students, those economically disadvantaged and employees will not be excluded from this study if they are otherwise eligible to participate. We will ensure that all informed consent such

PROTOCOL TITLE:
Making Treatment Decisions Using Genomic Testing

that they will be asked to repeat back the purpose of the study after a member of the study team has gone over written informed consent. In addition, although we will be providing incentives for participation in the form of a gift card the incentives are not so large as to be coercive.

12.0 Local Number of Subjects

60

13.0 Recruitment Methods

- 13.1 *Participants will be recruited via phone call, identified as below, by research staff.*
- 13.2 *Participants will be drawn from breast clinics at LCCC, Moffitt Cancer Center, and WHC.*
- 13.3 *PI/Collaborators will recruit participants from his/her/their own patient population.*
- 13.4 *Study materials include participant information/consent and interview done over a phone call. It will also include mailed introductory contact letter, informed consent form, study information sheet, and HIPPA waiver to be physically signed by participants.*
- 13.5 *Participants will receive a \$20 gift card to thank them for their time completing interviews and \$25 for recording of their clinical encounter.*

14.0 Withdrawal of Subjects*

- 14.1 Reason for withdrawing include lack of time and not being interested in participating in research related to breast cancer.
- 14.2 N/A
- 14.3 Participants will be informed that they can withdraw from the study at any time. We will track the number of eligible participants that withdraw. Data from participants that withdraw from the study will not be used.

15.0 Risks to Subjects*

- 15.1 The primary sources of risk concerns data privacy, confidentiality, and psychological discomfort. There are few psychological risks to completing cognitive, decision making, and psychological assessments. However, interviews may contain questions that make participants feel uncomfortable or bring up unwanted thoughts or feelings. There is also minimal risk that using the QPL will increase any psychological distress. All participants will be informed in advance of participation and each data collection opportunity that any questions that make them feel uncomfortable may be skipped or ignored.

The risk of gathering social, behavioral, and medical information is also present.

PROTOCOL TITLE:
Making Treatment Decisions Using Genomic Testing

There is some risk for breach of confidentiality. However, we have taken multiple steps to ensure this risk is very low. Only key staff members will have access to individually identifiable private information about participants, including the principal investigator, the project coordinator, and research assistants. We also developed a rigorous data management plan to reduce this risk.

16.0 Potential Benefits to Subjects*

16.2 There is no direct benefit to individual subjects.

17.0 Data Management* and Confidentiality

17.1 We will calculate descriptive and frequency distributions for all variables. We will assess the quality of the data and evaluate the extent and impact of missing data. For categorical variables, we will use Chi-Square tests or Fisher's exact tests if needed. We will test continuous variables with Student t-tests or Mann-Whitney U tests for non-normal data. Any variable that exhibits a $p < .10$ association with the key predictors or outcomes will be controlled in multivariable analyses. Potential covariates include sociodemographic and clinical variables as well as differenced.

Our primary endpoint is the percentage of patients activated via a question prompt list intervention. Women will demonstrate significant increase in comprehension from pre- to post-QPL.

Using a 2-tailed $\alpha = 0.05$ and assumed a minimum of 75 participants at T2 and accounting for clustering by oncologist, we calculated effective sample sizes assuming an average cluster size of 10 patients per oncologist and an ICC of 0.02. This reduces the sample size by a factor of 1.18, leaving an effective $N = 64$ at T2. We will have 80% power to detect changes in mean comprehension of 0.4 SD assuming a correlation of 0.5 between pre- and post- scores. We will use multilevel models to address the clustering of observations within patients and of patients within oncologists. These mixed effects regression models will include random effects for patient and oncologist and fixed effects for time, the main predictor, and covariates. The multilevel model for 2a will be a linear model and we will estimate the adjusted mean change in comprehension and the corresponding 95% confidence interval. We will estimate an adjusted odds ratio with the corresponding 95% confidence interval.

17.2 Data collected in this study will be used exclusively for research purposes; it will be managed and stored according to our sites' security standards for data that require the highest possible security to ensure there will be no inadvertent disclosure. Any computers storing or accessing data collected for the study will be required to comply with these standards.

During the trial, all study data downloaded from REDCap or gathered from other sources will reside in a HIPAA-compliant study folder. Access to the study folder is provided based

PROTOCOL TITLE:

Making Treatment Decisions Using Genomic Testing

on employee's role, on a 'need to know, least privilege' basis. Georgetown BOX is a secure (HIPAA/PHI approved) place to store study files.

No identifying data will be stored on laptop computers or other mobile computing hardware. Computers used to access the data will be protected by a username and password that meet our IT departments' complexity and change requirements to ensure a high degree of security, and they will be protected with anti-virus software and scanned regularly for vulnerabilities.

[REDCap](#) (Research Electronic Data Capture) is a research tool developed at Vanderbilt University as a secure web application to allow users to build and manage online surveys and databases, and to support data capture for research studies. It is a secure, IRB-approved, web-based application designed for managing online surveys and for communication between study sites. A locally hosted instance of REDCap will be used to store study data (Surveys, selected clinical data and tracking information such as participant names, phone numbers, address, etc). Questionnaires or other paper forms collected from each participant will be identified solely by participants' confidential study identification number and stored in a locked filing cabinet in study offices.

All study staff members will be trained to use these procedures, which will be detailed in a study manual of operating procedures. We have found that using these procedures provides a high degree of protection with respect to the privacy of individuals and the confidentiality of data.

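### The uncapped p<.10 covariate screen in 75 women should give way to a short list fixed in advance; the harm is confined to Aim 3 and is modest

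*Combined protocol and SAP*

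**What the plan says.** Section 17.1 gives the rule: any variable with a p<.10 "association with the key predictors or outcomes will be controlled in multivariable analyses". The tests named just before it are one-variable tests: "For categorical variables, we will use Chi-Square tests or Fisher's exact tests if needed" and "We will test continuous variables with Student t-tests or Mann-Whitney U tests for non-normal data". On the pool of candidates it says only: "Potential covariates include sociodemographic and clinical variables as well as differenced". That sentence stops short in the text available. No closed list, no maximum number and no obligatory covariate is given.

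Section 6.4 supplies the likely pool. For sociodemographics: "We will assess age, race/ethnicity, education, marital, employment, income, insurance status, comorbidity, and family cancer history". For disease variables: "We will assess diagnosis date, pathology (staging, grade, ER/PR/HER2), treatments, and dates". The Recurrence Score is also collected, and the oncologist's race, ethnicity and gender are recorded "for our measurement of concordance".

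The models in 17.1 are mixed models with random patient and oncologist effects. Time, the main predictor and the covariates enter as fixed effects, and no covariate-by-time term is mentioned. An adjusted mean change is promised for Aim 2a, and an adjusted odds ratio whose outcome and predictor are not named. Section 2.2 links three features of the encounter to three outcomes under Aim 3. No effect size, power or concordance rate is given for that aim.

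**The concern.** The rule lets the sample that tests the Aim 3 hypotheses also choose the adjustment set. With many candidates and a lenient threshold, several covariates will enter by chance. Each uses a degree of freedom and adds noise. In a small binary model, extra terms also push a non-null odds ratio away from 1. Whether a clinically relevant variable such as the Recurrence Score is adjusted for would depend on its p-value in 75 women. The wording does not say whether a model screens only its own predictor and outcome or all of them, so two analysts could follow 17.1 and report different Aim 3 models. At stake are the precision and reproducibility of the Aim 3 estimates.

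**Working it through.** **The plan's own figure.** 17.1 states 80% power for a 0.4 SD change at an effective N of 64.
- Design effect: 1 + (10 − 1) × 0.02 = 1.18, and 75/1.18 = 63.6, so 64 is reproduced.
- With a pre-post correlation of 0.5, the SD of change is √(2 × (1 − 0.5)) = 1 SD. Then 0.4 × √64 = 3.2 and 3.2 − 1.96 = 1.24, which gives power of about 89% (88% with a t-test).
- The change detectable with 80% power is 0.35 SD. The statement is therefore conservative. It concerns Aim 2a only and does not bear on the covariate rule.

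**Candidates.** Section 6.4 gives 9 sociodemographic items, about 6 disease items and the Score: about 16. This count is an assumption, since the plan has no closed list; 15 to 20 is a fair range.

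**Chance entries, if all candidates are noise and the tests independent.**
- Narrow reading (the model's own predictor and outcome): 1 − 0.9² = 0.19, and 16 × 0.19 = 3.0. The range is 2.9 (15 candidates) to 3.8 (20). The chance of at least one entry is 1 − 0.81¹⁶ ≈ 97%.
- Broad reading (three predictors and three outcomes): 1 − 0.9⁶ = 0.469, and 16 × 0.469 = 7.5. The range is 7.0 to 9.4. Simulated counts run slightly lower, about 7 for 16 candidates.

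**Power of the Aim 3 linear models.** Simulation with assumed r = 0.30, 15 candidates and the narrow screen; n = 64 stands in for clustering.

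| Setting | n | Unadjusted | Three fixed | Screened | Fixed − screened |
|---|---|---|---|---|---|
| All noise | 64 | 67.9% | 65.6% | 61.4% | 4.2 |
| All noise | 75 | 75.6% | 73.9% | 71.0% | 2.9 |
| Three fixed terms prognostic (r = 0.25 each) | 64 | 68.5% | 76.0% | 69.5% | 6.5 |
| Three fixed terms prognostic (r = 0.25 each) | 75 | 75.0% | 82.9% | 78.0% | 4.9 |

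With a true effect of zero, the screened model rejects in 4.9% to 5.5% of trials.

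**Aim 3 cross-sectional concordance odds ratio.** Simulation with n = 75, assumed true odds ratio 2, 25% non-concordant and noise covariates.
- Two fixed covariates: median 2.09 to 2.14 across runs.
- Narrow screen: 2.12 to 2.24, little different.
- Broad screen, 16 candidates: 2.34 to 2.36. That is 2.34/2.14 = 1.09 to 2.36/2.09 = 1.13 times the fixed-list value, and about 17–18% above the true 2.
- With 20–40% non-concordant, screening raises the odds ratio over the unadjusted one by about 3 to 11%. With a true odds ratio of 1 there is no inflation.

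The reason is sparse events. At 25% non-concordance, 75 × 0.25 ≈ 19 women are in the smaller group. One predictor plus two covariates leaves 19/3 ≈ 6 events per slope; one plus seven leaves 19/8 ≈ 2.

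**Aim 2 pre-post odds ratio.** In a random-intercept logistic model the screen changes it by at most about 1.3% (for example 3.27 to 3.31 for a true odds ratio of 3).

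**Aim 2a mean change.** With both interviews present, subtracting T1 from T2 cancels the patient effect, the oncologist effect and every time-invariant main effect, leaving the time coefficient and residual error. Numerically, the adjusted and unadjusted time coefficients differ by no more than 2 × 10⁻¹⁵. If 10–20% of T2 values are missing and T1 is kept, the estimate shifts by at most 0.01 to 0.03 SD.

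The simulations used independent continuous covariates and no oncologist effect.

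**The case against.** The best defence is that the study is about feasibility, that Aim 3 explores potential mechanisms, and that the only powered analysis, the comprehension change, is untouched. On the narrow reading, about 3 covariates enter and the odds ratio barely differs from that of a fixed pair. All of this stands, and it limits the weight of the point. It does not supply a reason to keep the screen.

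Several stronger readings are tempting, but the documents do not support them:
- **That the screen inflates the concordance odds ratio in general.** The odds-ratio sentence in 17.1 follows the mixed model with time and patient effects, and the pre-post odds ratio from that model hardly moves. Only the Aim 3 cross-sectional odds ratio is affected, and only when a real effect exists.
- **That seven or more chance covariates will enter.** This needs all six screens to feed every model. 17.1 does not say so.
- **That screening always costs power.** Against no adjustment it can gain when some candidates are prognostic (75.0% to 78.0% at n = 75). The loss is against a well-chosen fixed list.
- **That Aim 2a is biased.** An unchanged estimate is not a biased one. The identity also needs complete pairs and time-invariant covariates. Withdrawn women's data are dropped (14.3), but questions may be skipped (15.1), and Table 1 collects disease and treatment data at both interviews.
- **That scales would be dichotomized for screening.** The named tests do compare groups, but no cut-point is planned.
- **That oncologist-level variables pass far too often.** At the plan's ICC of 0.02 the pass rate is about 13% against a nominal 10%. A rate of 40% needs an assumed ICC of 0.3, and 17.1 does not name these variables as covariates.

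One further objection stands and shapes the fix: a long fixed list is no cure in the binary model. Six fixed noise terms gave a median odds ratio of 2.19 at n = 75, so the number of terms matters there more than the act of fixing them.

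**Conclusion.** The concern holds in a limited form. The rule in 17.1 is uncapped and data-driven, and a short fixed list is better. Chance alone admits about 3 covariates per model on the narrow reading and about 7 on the broad one, for about 16 candidates. Against a fixed list, the Aim 3 linear models lose roughly 3 to 7 points of power, with type I error near 5%. The Aim 3 cross-sectional concordance odds ratio shifts little on the narrow reading and up to about 10–20% on the broad one.

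These sizes rest on figures that the documents do not give: the candidate count, r of about 0.3, a true odds ratio of 2, and 20–40% non-concordance. For Aim 2a the label of an adjusted change adds nothing when pairs are complete. This is a cheap improvement to secondary analyses and does not threaten the study's main purpose.

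**What to change.** In 17.1, replace the p<.10 rule as follows:
- For the Aim 3 linear models, name a short list now on subject-matter grounds, for example age, education and the continuous Recurrence Score.
- For the binary concordance model, name a separate set of at most two single-degree-of-freedom terms, for example age and education. Leave the Score out where the outcome is defined from it. Settle that definition first: 2.2 speaks of concordance with the Score, while 6.4 matches preference to the treatment received.
- Report the Aim 2a mean change without covariates as the main estimate.
- Keep any screened-covariate model as a labelled sensitivity analysis, and say which predictors and outcomes are screened.

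The cost is a change of wording, with no added data or participants. The downside is that unforeseen associations are dealt with only in sensitivity analyses.
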